7.3 Random Assignment

Eligible participants will be randomly assigned to study condition (VI, PNV, DE) in a 1:1:1 strategy using an urn randomization procedure (Stout et al., 1994) to provide multivariate balance across two characteristics correlated with outcomes in addiction treatment trials: type of opioid (heroin or prescription drug) and gender.

Individuals who terminate participation before induction onto the assigned medication (or similar time-point for behavioral assignments) will be replaced. Those terminating after VI induction or provision of the first DE session will not be replaced and will be counted as "treatment failures" (in an intent-to-treat scenario).

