7.6.2 Patient Navigators (PN)

In addition to receiving Vivitrol, participants in the PNV condition will be assigned a Patient Navigator (PN). A PN provides one-on-one assistance to surmount barriers to entry and adherence with medical care for chronic disease. Originally designed to improve outcomes in oncology for disadvantaged female patients, the PN conceptual foundation is a strengths-based case management perspective to help patients keep their appointments (through scheduling, reminders, and accompanying the patients), improve communication between the patient and their providers, offer health education, provide assistance with personal barriers to treatment (e.g., transportation, health insurance, childcare), and offer emotional support. Clinical trials have found that PN increased cancer screening and follow-up rates, improved entry and adherence to HIV treatment, and increased adherence to medical appointments and greater likelihood of achieving an undetectable viral load compared to controls.

Addictions treatment studies have also found positive outcomes in randomized trials for services comparable to PN to increase the likelihood of treatment entry from: a central drug treatment intake; receiving medical care at a hospital; and community outreach. Although a case

management approach was not found effective in linking drug users newly-released from prison to community treatment, that study's sample was heterogeneous in terms of its drug use (only 10% were opioid-dependent) and did not receive pharmacotherapy. PN has not been studied in re-entry into the community with treatment initiated in jail. It is our hypothesis that PN has the potential to assist newly-released detainees to overcome barriers to successful community treatment entry.

In this study, the Patient Navigator (PN) will meet with PN participants to discuss barriers to treatment, facilitate referrals to community outpatient behavioral drug abuse treatment, and provide assistance with other social support-related needs.

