10.0 STATISTICAL ANALYSES

The project emphasizes evaluation of the clinical utility of Vivitrol in jail inmates as compared with a Drug Education condition (DE), while descriptive statistics will provide an overall assessment of the implementation of the protocol.

Analyses will include an Intent-to-treat (ITT) design such that all randomized participants who received at least one dose of medication (VI, PNV), or received at least one session of drug education (DE) will be included who did not violate the protocol in a way that could potentially affect the efficacy results. Participants will be excluded from the Protocol Population (PP) if:

- 1. concomitant medication that is known to have significant clinical effect on primary or secondary endpoints was administered.
- 2. Violations of the inclusion or exclusion criteria are judged to affect the efficacy evaluations.

Subjects in the PP population will be allocated to treatment groups in the analysis based on the actual treatment they received. If there is substantial difference between the ITT population and the PP population, all analyses described below will be performed using only subjects in this group.

All statistical tests will be performed using two-sided .05 significance levels, unless otherwise stated. All comparisons between treatments will be reported with parameter estimates and 95% confidence intervals. For parameters measured at baseline and subsequently, the variables of interest are changes from baseline.

Post-baseline variables will not be imputed; estimates can be obtained using the hierarchical models specified below under the assumption of missing at random. For the primary outcome measure, diagnosis at six months, subjects who have dropped out for whatever reason will be considered to retain the diagnosis. Other outcome measures for which data are missing will be imputed using multiple imputation methods. Sensitivity analyses will repeat specific analyses using permutation tests of at least 1000 samples.

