10.3 Power and Sample Size

With the primary focus of this study on the feasibility and clinical utility of the two pharmacotherapies, the study is not powered to be an exhaustive comparison but to parsimoniously enable preliminary characterization of outcomes that will be needed to inform a future, larger scale multi-site trial. We expect that a baseline sample of 150 participants with 50 participants per condition will yield a final aggregate sample of approximately 120 participants. assuming 10-20% dropout. (Our similar studies have had 85-90% follow-up rates.) Thus, a final evaluable sample size of 120 participants would permit detection of a medium-large effect size (~.60) between conditions for some of the outcome variables (at ~.70 power) and .5 effect size (at .80 power) for others. For example, we expect that the measure "time to first opioid use" will be markedly different among the three groups, given the difference given the expected relapse among the no-medication group. Over time, the total number of opioid-free urine results is expected be greater among the VI participants, who are likely to show less dropout and better long-term retention compared to the DE group. Our selection of the effect size is based on effects found in the literature for Vivitrol when compared against placebo, and is consistent with both Cohen (1988) and with more recent guidance; for example, Lipsey and Wilson (1993) did a meta analysis of 302 meta-analyses that included over 10,000 studies and found that the average effect size was .5, adding support to Cohen's recommendation that selection of the effect size of .5 is appropriate (Bausell & Li, 2002).

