10.4.2 Primary Statistical Analysis of the First Primary Outcome Measure

A mixed effects logistic regression will used to model the binary primary outcome measure; the diagnosis of opioid use disorder at six months post treatment. are modeled as a linear combination of predictor variables. A logit link function will be used to link subject covariates to the probability of success There will be two levels in the model: within sites and between sites. The model will included treatment, cluster (site) and baseline covariates as fixed effects and subject as a random effect. Indicator variables will identify whether a subject has received XR-NTX, methadone and a behavioral intervention (PN.) Site by treatment interactions will be included in the model. Interactions that are statistically significant at the 10% level will be investigated and may imply that analyses of individual sites is required. In this case, relevant contrasts will be performed within the sites.

Additional covariates will include age, gender, whether a subject had prior methadone maintenance treatment and baseline self-reported cocaine use. Other possibilities mediating

factors include opioid dependence severity at baseline, concurrent cocaine or alcohol and/or benzodiazepine misuse, and homelessness.

SAS PROC Mixed will be used to perform the analysis. The coefficients in the model will be estimated by generalized least squares (GLS), with covariance parameters estimated by restricted maximum likelihood (REML). Standard errors of the parameter estimates will be computed using the model. This procedure assumes that missing observations are ignorably missing or missing at random (MAR).

The primary contrast is a comparison of the probability of a DSM-5 Opioid Use Disorder Diagnosis at 6 months for those on medication versus those receiving enhanced treatment as usual (etau.) The contrast will utilize XR NTX data from both the NYU and UCLA and Interim Methadone data from FRI; the medication plus PN treatment arm will not be included.

Descriptive statistics will examine feasibility issues of the pharmacotherapy, analyzing AEs, side effects, and patient and clinician acceptance, and reasons for early termination or post-randomization refusal of assigned condition. Single-point, between-group comparisons of these measures can be tested using t-tests or ANOVAs for continuous variables and chi-square for binary measures.

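### Scoring every dropout as still diagnosed can favour Vivitrol over drug education if more month-6 diagnoses are missing in DE, and no planned analysis varies that assumption

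*Combined protocol and SAP*

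**What the plan says.** Section 10.0 sets the rule for the primary diagnosis: "subjects who have dropped out for whatever reason will be considered to retain the diagnosis". Section 7.3 points the same way: "Those terminating after VI induction or provision of the first DE session will not be replaced and will be counted as" treatment failures.

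Section 10.3 forecasts retention. It plans "a baseline sample of 150 participants with 50 participants per condition", "assuming 10-20% dropout", and adds that "Our similar studies have had 85-90% follow-up rates". It describes the VI participants as people "who are likely to show less dropout and better long-term retention compared to the DE group". It gives no dropout figure for any single arm.

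Other sentences on missing data do not fit the rule. The sentence just before it in 10.0 rules out imputing post-baseline variables and relies on missing at random; the sentence just after it calls for multiple imputation of the other outcomes. Section 10.4.2, on the model for this same diagnosis, says: "This procedure assumes that missing observations are ignorably missing or missing at random (MAR". Section 10.4.1 also allows case elimination or mean substitution. The only sensitivity analysis named in 10.0 is a set of permutation tests.

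Section 7.13 lets participants who stop medication keep attending and complete assessments, so stopping treatment need not mean that the month-6 diagnosis is missing.

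**The concern.** Counting missing as failure is often defended as conservative. It is conservative for the medication only if the medication arm loses at least as many participants as the comparator. Here the plan forecasts the reverse. If that forecast carries over to the month-6 interview, part of any advantage for VI on the primary diagnosis would be better attendance scored as absence of disorder. If loss is equal, the rule pulls a real difference towards zero.

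Nothing planned would show which of these had happened. Once failures have been filled in, no diagnosis is missing, so the missing-at-random statement does no work and assumed values are analysed as observed. A permutation test re-draws treatment labels on the same filled-in data, so it checks the reference distribution of the test and not the values assigned to those lost. Two analysts could also follow different sentences of the plan and report different primary results.

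**Working it through.** **The plan's own figure.** 150 × (1 − 0.20) = 120, the evaluable sample in 10.3. At 10% dropout it would be 150 × 0.90 = 135. The stated 120 therefore uses the upper end of the range.

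**Inputs from the documents.** 50 per arm and 10–20% dropout (10.3); two-sided 0.05 (10.0); every dropout scored as diagnosed (10.0).

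**Assumptions.** The true month-6 rate and the loss by arm are not given. I take a common true rate p from 0.3 to 0.8 in both arms (no treatment effect), and loss of 10% in VI and 20% in DE, the two ends of the stated range. The comparison is VI versus DE at this site, by an unadjusted pooled z test, with rejection probabilities from exact binomial enumeration.

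**Formula.** If those lost resemble their arm, the scored rate is p + d(1 − p), where d is the loss. The spurious difference is (1 − p)(d_DE − d_VI). Example at p = 0.5: VI 0.5 + 0.10 × 0.5 = 0.55; DE 0.5 + 0.20 × 0.5 = 0.60; difference 5 points.

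| True rate, both arms | Scored VI | Scored DE | Spurious difference | Significant for VI | Two-sided error |
|---|---|---|---|---|---|
| 30% | 37% | 44% | 7 points | 11.0% | 11.4% |
| 40% | 46% | 52% | 6 points | 9.6% | 10.2% |
| 50% | 55% | 60% | 5 points | 7.8% | 8.5% |
| 60% | 64% | 68% | 4 points | 6.1% | 6.9% |
| 70% | 73% | 76% | 3 points | 5.3% | 6.4% |
| 80% | 82% | 84% | 2 points | 4.8% | 6.3% |

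The nominal chance of a significant result for VI is 2.5%. With equal loss of 15% in each arm, the spurious difference is zero and the two-sided error of this test is 4.9% to 5.7%. With equal loss of 10% at p = 0.5 it is 5.6%. The excess over that at 10% versus 20% is therefore about 3 percentage points (8.5 − 5.6 = 2.9).

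**If those lost have relapsed more often.** Hold the overall true rate at 50% in both arms and let a fraction q of those lost have the disorder. The scored rate is then 0.5 + d(1 − q), and the spurious difference is (1 − q)(0.20 − 0.10).

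| q among those lost | Scored VI | Scored DE | Spurious difference | Two-sided error |
|---|---|---|---|---|
| 50% | 55% | 60% | 5 points | 8.5% |
| 75% | 52.5% | 55% | 2.5 points | 6.4% |
| 90% | 51% | 52% | 1 point | 5.8% |
| 100% | 50% | 50% | 0 | no bias |

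**If there is a true effect.** Take true rates of 40% (VI) and 60% (DE), a 20-point difference, with those lost resembling their arm. Equal 15% loss: 0.40 + 0.15 × 0.60 = 49% and 0.60 + 0.15 × 0.40 = 66%, so 17 points. Loss of 10% and 20%: 46% and 68%, so 22 points.

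**The case against.** *Unequal loss of the month-6 diagnosis is an inference.* The retention forecast in 10.3 appears in a remark about opioid-free urines and has no figures. DE has the same visit schedule as the other arms, all arms get weekly calls (2.2), visit payments do not differ by arm (7.15), and people who stop medication can still be assessed (7.13). This stands. It makes the bias conditional, but it does not rule the bias out, and the plan offers no other forecast.

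*Most of those lost may well have relapsed.* Section 4.1 calls a return to drug use after release the norm. This also stands: as the second table shows, the bias then nearly vanishes. It is also why missing at random may be wrong here, so a demand that multiple imputation become the primary rule would go too far. Reasonable statisticians would differ on that choice.

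*The calculation is not the planned test.* The contrast in 10.4.2 pools extended-release naltrexone data from two groups with interim methadone data from a third, in a site- and covariate-adjusted model. Retention elsewhere is not in the documents, so the error of that contrast is unknown.

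*The navigator.* A reader might infer that the Vivitrol-plus-navigator arm (PNV) widens the bias, since section 7.6.2 describes the navigator's role as to "help patients keep their appointments (through scheduling, reminders, and accompanying the patients"). But 10.4.2 leaves PNV out of the primary contrast, so this cannot be charged to it.

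*Already handled.* Section 10.4 plans a survival analysis of retention, which could reveal unequal loss, and the failure rule covers only the diagnosis, not the other primary outcome, opioid use. Both are true. Neither shows how far the primary result depends on the rule.

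*The specific sentence governs.* The rule in 10.0 can be read as an exception to the general statement, in line with 7.3. That is the likeliest intent, but 10.4.2 restates missing at random for this very endpoint, so the text still needs reconciling.

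**Conclusion.** The concern holds in a conditional form and should be fixed. The rule favours VI over DE if more month-6 diagnoses are missing in DE and not everyone lost has the disorder. At 10% versus 20% loss and no true effect, the size is modest: 2 to 7 points, and a two-sided error of about 6% to 11%. At a true rate of 50%, the error falls from 8.5% to 6.4% or 5.8% if 75% or 90% of those lost have the disorder. These figures rest on assumed loss and diagnosis rates, VI versus DE at this site alone, and an unadjusted test.

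Two stronger readings are not supported. One is that a medication benefit is built into the endpoint: equal loss, or relapse in everyone lost, removes the bias, and equal loss works against a true effect. The other is that the error reaches the levels seen with wider gaps: at p = 0.5 the same calculation gives 18.0% for 10% versus 30% loss and 34.4% for 10% versus 40%, but both put DE loss above the 10–20% that the plan assumes.

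Two defects need no assumed rates: the conflicting missing-data statements for one primary endpoint, and the absence of any sensitivity analysis that varies the missing-data assumption.

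**What to change.** In 10.0 and 10.4.2:

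- State one missing-data rule for the diagnosis, and remove the no-imputation and missing-at-random wording where it conflicts with that rule. The failure rule may remain primary if the team prefers it.
- State that the rule applies only when the month-6 diagnosis is missing. An observed diagnosis is used even if medication was stopped, in line with 7.13; align the treatment-failure wording in 7.3.
- Prespecify two sensitivity analyses: multiple imputation of the diagnosis by assigned arm, using earlier TLFB, urine-screen and craving data; and a tipping-point table that varies the diagnosis rate among the missing separately by arm.
- Report month-6 missingness by arm beside the primary result, and do not describe a benefit as robust if it depends on the failure rule.

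The cost is SAP wording and some extra programming on data already scheduled for collection. The downside is that the conclusion may have to be stated less firmly.

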10.1 Primary Outcome

The primary outcomes of opioid use and a DSM-5 diagnosis of opiate use disorder 6 months after randomization.

10.2 Secondary Outcomes

Analyses will include descriptive, binomial and multinomial methods to address secondary outcomes:

- HIV risk behaviors (compared using repeated measures procedures to evaluate possible change in sexual and drug-related behaviors that may inhibit or promote HIV infection) measured by the HIV-GAIN;
- (2) Self-reported number of days incarcerated during the intervention and follow-up phases;
- (3) Self-reported number of days of opioid and other drug use measured by TLFB, and

objective measures of drug use by urine drug screens (UDS) at the 6-month post-release assessment (end of the intervention phase);

- (4) Self-reported days in drug abuse treatment;
- (5) Self-reported number of arrests;
- (6) Self-reported craving for opioids;
- (7) Self-reported number of overdoses; and
- (8) Self-reported motivation for treatment.

10.3 Power and Sample Size

With the primary focus of this study on the feasibility and clinical utility of the two pharmacotherapies, the study is not powered to be an exhaustive comparison but to parsimoniously enable preliminary characterization of outcomes that will be needed to inform a future, larger scale multi-site trial. We expect that a baseline sample of 150 participants with 50 participants per condition will yield a final aggregate sample of approximately 120 participants. assuming 10-20% dropout. (Our similar studies have had 85-90% follow-up rates.) Thus, a final evaluable sample size of 120 participants would permit detection of a medium-large effect size (~.60) between conditions for some of the outcome variables (at ~.70 power) and .5 effect size (at .80 power) for others. For example, we expect that the measure "time to first opioid use" will be markedly different among the three groups, given the difference given the expected relapse among the no-medication group. Over time, the total number of opioid-free urine results is expected be greater among the VI participants, who are likely to show less dropout and better long-term retention compared to the DE group. Our selection of the effect size is based on effects found in the literature for Vivitrol when compared against placebo, and is consistent with both Cohen (1988) and with more recent guidance; for example, Lipsey and Wilson (1993) did a meta analysis of 302 meta-analyses that included over 10,000 studies and found that the average effect size was .5, adding support to Cohen's recommendation that selection of the effect size of .5 is appropriate (Bausell & Li, 2002).

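### The .80 power stated for an effect size of .5 does not follow from the plan's inputs: 40 evaluable per arm give about 60% for an unadjusted pairwise comparison

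*Combined protocol and SAP*

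**What the plan says.** Section 10.3 starts from 150 randomised, 50 per condition, and arrives at about 120 evaluable "assuming 10-20% dropout". It then gives two pairs of effect size and power at that number. The first is that "a final evaluable sample size of 120 participants would permit detection of a medium-large effect size (~.60) between conditions for some of the outcome variables"; its power is put at roughly .70. The second is "and .5 effect size (at .80 power) for others". Neither pair is tied to a named outcome, test, contrast, standard deviation, correlation or number of repeated measures. The section ends by citing the literature to argue "that selection of the effect size of .5 is appropriate".

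The other inputs are elsewhere. Section 7.3: "Eligible participants will be randomly assigned to study condition (VI, PNV, DE) in a 1:1:1 strategy". Section 10.0: "All statistical tests will be performed using two-sided .05 significance levels, unless otherwise stated". Section 10.0 also says: "For parameters measured at baseline and subsequently, the variables of interest are changes from baseline". Section 10.4 lists t-tests and ANOVAs for craving and psychological scores, and says that secondary analyses may include longitudinal models.

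**The concern.** For any single test at a single sample size, a smaller effect has less power. The sentence pairs the smaller effect (.5) with the higher power (.80) and the larger effect (about .60) with the lower power (about .70), both at 120 evaluable. Different outcomes could in principle be analysed in ways that differ this much, but the plan does not say what differs.

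What is at stake is how the results are read. The plan treats .5 as its reference effect and says the findings will inform a larger multi-site trial. A reader who accepts .80 would take a non-significant comparison as carrying a 20% risk of missing an effect of .5. For an unadjusted pairwise comparison the risk is about 40%.

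**Working it through.** **Inputs**
- Two-sided alpha .05 (10.0).
- Three arms, 1:1:1 (7.3); 150 randomised, 50 per arm (10.3).
- 120 evaluable (10.3), so 120/3 = 40 per arm. The 40 is derived, not stated. It corresponds to 20% dropout; 10% gives 45 per arm.
- Effect size .5 (10.3), read as d, the mean difference divided by the SD. This is an assumption.

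**Formula.** For groups of n1 and n2, the noncentrality is δ = d × √(n1·n2/(n1+n2)). Power is the probability that a noncentral t with n1+n2−2 degrees of freedom and noncentrality δ exceeds the two-sided .05 critical value in absolute size.

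**Attempt to reproduce .80 at d = .50**

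| Comparison | δ | Power |
|---|---|---|
| Pairwise, 40 v 40 | .5 × √20 = 2.236 | .598 |
| Pairwise, 45 v 45 (10% dropout) | .5 × √22.5 = 2.372 | .650 |
| Pairwise, 50 v 50 (no dropout) | .5 × √25 = 2.500 | .697 |
| Pooled medication v DE, 80 v 40 | .5 × √26.67 = 2.582 | .726 |
| Pooled, 90 v 45 (10% dropout) | .5 × √30 = 2.739 | .776 |
| Pooled, 100 v 50 (no dropout) | .5 × √33.33 = 2.887 | .818 |

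Taking the 40 v 40 contrast from a three-arm model (117 error degrees of freedom) gives .602.

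A three-group ANOVA with means 0, .5, .5 has f = .236, the SD of the three means over the common SD. Its power is .621 at N = 120, .677 at 135 and .727 at 150.

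Only the pooled comparison with all 150 analysed passes .80, and that is not the stated 120.

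**Inverting the calculation.** Power of .80 needs d = .634 at 40 v 40 and d = .547 at 80 v 40. Pairwise power of .80 at d = .50 needs 63.8, so 64, evaluable per arm.

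**The companion figure.** At 40 v 40, d = .60 gives .755 and d = .56 gives .696. The statement of about .60 at about .70 is therefore roughly right and slightly conservative, and I do not challenge it.

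**Routes that could reach .80 at d = .50.** Each needs a correlation that the documents do not give.
- *Baseline adjustment*, effective d = .5/√(1−r²). At 40 v 40, .5/√(1−r²) = .634 gives r = .62. At 80 v 40, with target .547, r = .41.
- *Change from baseline*, effective d = .5/√(2(1−r)). At 40 v 40, r = .69. Below r = .5 a change score lowers power.
- *Mean of k post-baseline measures* with constant within-person correlation ρ, effective d = .5/√((1+(k−1)ρ)/k), at 40 v 40:

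| k | ρ = .4 | ρ = .5 | ρ = .6 | ρ giving .80 |
|---|---|---|---|---|
| 3 (months 1, 3, 6) | .814 | .772 | .732 | .43 |
| 5 (all assessment visits, 5.2) | .865 | .814 | .764 | .53 |
| 9 (medical management visits, 7.15) | .898 | .842 | .786 | .57 |

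**The case against.** The strongest reply is that the .80 is claimed only for unnamed other outcomes, and that a single-timepoint pairwise t-test is not the plan's only analysis. Section 10.2 has repeated-measures procedures for HIV risk, and 10.4 has aggregate urine scores, survival models and mixed models. Some of these could reach .80. That stands, and it limits the finding to saying that the figure is unsupported; it does not show that the figure is unattainable. It does not supply the missing correlation or tie the .80 to any of these analyses.

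The ANOVA result depends on the assumed pattern of means. With 0, .5, .7 it would be .821 at N = 120. But that pattern contains a difference larger than .5, so it does not reproduce the stated pair.

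The .5 might be a hazard ratio, since 10.3 mentions time to first opioid use. On that reading .80 power needs about 65 events pairwise or 74 pooled, which is possible if relapse is common. However, the medium-large label, the appeal to Cohen and the cited average effect size of .5 all point to a standardised mean difference.

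Finally, 10.3 describes the study as preliminary and not powered for exhaustive comparison. That is a fair reason not to ask for a larger trial. It does not make the stated power correct.

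**Conclusion.** The concern holds. On the plan's stated inputs, power at d = .50 for a continuous outcome is .598 pairwise, .621 for the three-group ANOVA with means 0, .5, .5, and .726 for pooled medication against drug education, against .80 stated. No dropout rate within the plan's 10–20% range brings these comparisons to .80.

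This rests on reading the effect size as d, on equal evaluable numbers per arm, and on analyses with neither baseline adjustment nor repeated measures. It does not apply to the binary diagnosis outcome, because 10.0 says "subjects who have dropped out for whatever reason will be considered to retain the diagnosis", so 120 is not the number analysed there. It corrects a stated property of the design and is not an argument against the design.

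**What to change.** In 10.3, replace the second pair with a statement along these lines: with 40 evaluable per arm and two-sided .05, an unadjusted pairwise comparison of a continuous outcome has about 60% power for d = .50, 75% for d = .60 and 80% for d = .63. Define the effect size as a standardised mean difference, or name the metric that was meant.

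Keep a .80 figure for .5 only if the outcome, test, contrast and assumed correlation or number of repeated measures are stated beside it. If the authors have such a basis, stating it is enough.

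The cost is one sentence. Either the stated power at .5 becomes less favourable, or the supporting assumption becomes visible. Enrolment and the analyses stay as they are.
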